#### Safety and tolerability

All patients will be evaluable for toxicity from the time of their first treatment with any study agent. Toxicity will be graded according to NCI CTCAE, Version 5.0. Toxicities will be summarized by maximum grade and by treatment arm. Incidence rate of each toxicity will be reported with 95% exact CI. The incidence rates of any grade 3+ toxicity will be compared between two arms using Fisher's exact test.

#### Correlative endpoints

Recently, Herbst et al have demonstrated that patients who presented an increase of at least 5% in expression of PD-L1 in tumor microenvironment experienced a bigger likelihood to respond to treatment with the anti-PD-L1 Atezolizumab [Herbst *et al.*, 2014]. Also, modifications in molecular

signature of tumor microenvironment also correlated with response rate to this drug. Because of this rationale, we plan to perform two research biopsies in tumor lesion: one at baseline and the other one at day 29 cycle 1 of the experimental treatment.

With a sample size of 30 and assuming that there will be patients without accessible lesions, the table below indicates the power available to detect 20%, 30%, 40%, or 50% increases of PD-L1 positivity rate. The power calculation is based on McNemar’s test with 1-sided alpha of 0.05 and assuming 2% of patients unexpectedly show PD-L1 positivity only in the baseline assessment. The calculation was done using East v6.3 (Cytel Inc).

Increase of PD-L1 positivity rate post treatment	# of paired biopsies available	Power
20%	15	54%
	20	64%
30%	15	75%
	20	85%
40%	15	90%
	20	96%
50%	15	97%
	20	> 99%

PD-L1 positivity seen at baseline and C3D1 samples will be summarized using contingency tables. An exploratory analysis is planned to evaluate PD-L1 change in continuous scale.

### 13.5 Central confirmation of the tumor mutational burden

All patients who initiated protocol therapy will need to agree to undergo a research biopsy, if tumor is safely accessible, at baseline. Participants for whom newly-obtained samples cannot be provided (e.g. inaccessible or participant safety concern) may submit an archived specimen (block or if not possible, 20 unstained slides). The tumor mutational burden will be accessed by Foundation One panel that will be used as a central confirmation test for the cutoff of  $\geq 9$  Mut/Mb.

### 13.6 Reporting and Exclusions

#### 13.6.1 Evaluation of Efficacy

For this Phase II trial, the efficacy evaluable population is a modified intent-to-treat (ITT) population. The modified ITT population consists of all patients who initiate protocol therapy, even if there are major protocol therapy deviations. Patients that do not start protocol therapy will be considered unevaluable and will be replaced.

Subanalyses may then be performed on the basis of a subset of participants, excluding those for whom major protocol deviations have been identified (e.g., early death due to other reasons, early discontinuation of treatment, major protocol violations, etc.). However, these subanalyses may not serve as the basis for drawing conclusions concerning treatment efficacy, and the reasons for excluding participants from the analysis should be clearly

reported. If applicable to the endpoint, the 95% confidence intervals should also be provided.

#### 13.6.2 Evaluation of Safety

The safety population will be used in the safety data summaries. The safety population consists of all patients who took at least one dose of any randomized treatment and who have at least one post-baseline safety assessment. Note that a patient who had no adverse events constitutes a safety assessment. Patients who have received at least one dose of study drug but have no post-treatment safety data of any kind would be excluded.

### **14. PUBLICATION PLAN**

The results should be made public within 1 year of reaching the end of the study. The end of the study is the time point at which the last data items are to be reported, or after the outcome data are sufficiently mature for analysis, as defined in the section on Sample Size, Accrual Rate and Study Duration. If a report is planned to be published in a peer-reviewed journal, then that initial release may be an abstract that meets the requirements of the International Committee of Medical Journal Editors. A full report of the outcomes should be made public no later than three (3) years after the end of the study.

**APPENDIX A PERFORMANCE STATUS CRITERIA**

ECOG Performance Status Scale		Karnofsky Performance Scale	
Grade	Descriptions	Percent	Description
0	Normal activity. Fully active, able to carry on all pre-disease performance without restriction.	100	Normal, no complaints, no evidence of disease.
		90	Able to carry on normal activity; minor signs or symptoms of disease.
1	Symptoms, but ambulatory. Restricted in physically strenuous activity, but ambulatory and able to carry out work of a light or sedentary nature ( e.g. , light housework, office work).	80	Normal activity with effort; some signs or symptoms of disease.
		70	Cares for self, unable to carry on normal activity or to do active work.
2	In bed <50% of the time. Ambulatory and capable of all self-care, but unable to carry out any work activities. Up and about more than 50% of waking hours.	60	Requires occasional assistance, but is able to care for most of his/her needs.
		50	Requires considerable assistance and frequent medical care.
3	In bed >50% of the time. Capable of only limited self-care, confined to bed or chair more than 50% of waking hours.	40	Disabled, requires special care and assistance.
		30	Severely disabled, hospitalization indicated. Death not imminent.
4	100% bedridden. Completely disabled. Cannot carry on any self-care. Totally confined to bed or chair.	20	Very sick, hospitalization indicated. Death not imminent.
		10	Moribund, fatal processes progressing rapidly.
5	Dead.	0	Dead.

## **APPENDIX B            GUIDELINES FOR COLLECTING RESEARCH BIOPSY TISSUE**

Tissue specimens will be collected from metastatic lesions using standard institutional procedures. The amount of tissue collected may follow the guidelines listed below:

*Skin/chest wall:* A goal of 2 4-mm punch biopsies will be obtained.

*Lymph node:* A goal of 3-6 core biopsy specimens will be obtained using an 18-gauge needle.

*Liver:* A goal of 3-6 core biopsy specimens will be obtained using an 18-gauge needle.

*Lung:* Because of the risk of pneumothorax associated with core needle biopsies of lung nodules, no core biopsies of lung nodules are mandated on this protocol, unless they are clinically indicated.

*Bone:* Because the yield of malignant tissue from bone biopsies tends to be relatively low, if a patient has another accessible site of disease (i.e. skin, lymph node, liver), that site should be biopsied preferentially. If bone is the only biopsy-accessible site, then a goal of 3-6 core biopsy specimens will be obtained using an 11-13 gauge needle.

**Please note that the above are guidelines for the amount of tissue to be obtained, and are not meant to replace clinical judgment at the time the procedure is performed.** Less than the goal quantity of tissue is accepted for each type of biopsy, and will be left to the clinical judgment of the physician performing the procedure.

Coded laboratory specimens will be stored in the Tumor Bank of the DFCI. These specimens will become the property of DFCI. Patients will be informed that their specimens may be used for research by investigators at DF/HCC and other approved collaborators. Shared specimens will be identified with a sample ID number; all patient identifying material will be removed.

### **Risks of Research Biopsy and Procedures for Minimizing Risk**

#### **Potential risks according to site are:**

*Skin/chest wall (punch biopsy):*

- Likely: local discomfort and minor bleeding
- Less likely: moderate or major bleeding, or infection

*Lymph node, liver, or bone (core needle biopsy):*

- Likely: local discomfort and minor bleeding
- Less likely: moderate or major bleeding, need for blood transfusion, hospitalization due

to bleeding or other complications, infection, damage to adjacent organs. Additional risks may be present if intravenous conscious sedation is required

*Breast (core biopsy):*

- Likely: local discomfort and minor bleeding.

- Less likely: moderate or major bleeding, need for blood transfusion, hospitalization due

to bleeding or other complications, infection, pneumothorax, damage to adjacent organs.

*Pleural fluid (thoracentesis):*

- Likely: local discomfort and minor bleeding
- Less likely: moderate or major bleeding, need for blood transfusion, hospitalization due to bleeding or other complications, infection, pneumothorax, damage to adjacent organs

*Ascites fluid (paracentesis):*

- Likely: local discomfort and minor bleeding
- Less likely: moderate or major bleeding, need for blood transfusion, hospitalization due to bleeding or other complications, infection, bowel perforation or damage to adjacent organs. In order to minimize the risk of a biopsy, only qualified personnel will perform these procedures.

Prior to the procedure, the physician performing the procedure will discuss the risks with each study participant, answer any questions, and obtain separate procedure consent. Patients will be evaluated for comorbidities or concomitant medications that may increase the risk of potential complications. For biopsies of lesions that are not superficial and clearly palpable, imaging studies such as CT or ultrasound will be used to guide the biopsy in order to minimize the risk of damage to adjacent structures. After lymph node biopsies, patients will be observed a minimum of 2 hours (range 2-4 hours) after the procedure, or according to standard institutional guidelines. After liver biopsies, patients will be observed a minimum of 4 hours (range 4-6 hours) after the procedure, or according to standard institutional guidelines. Less than the goal quantity of tissue is accepted for each type of biopsy, and will be left to the clinical judgment of the physician performing the procedure.

## **Risks of Anesthesia**

### **Local Anesthesia**

All biopsy procedures require local anesthesia using lidocaine, xylocaine, or related compounds. There is a small risk of an allergic reaction associated with these drugs. In order to minimize the risk of local anesthesia, only qualified personnel will perform the biopsy procedure. Patients will be queried if they have had previous allergic reactions to local anesthetics.

### **Intravenous Conscious Sedation**

Certain biopsy procedures, such as lymph node, liver, or bone biopsies, may require intravenous conscious sedation (IVCS). IVCS is a minimally depressed level of consciousness that retains the patient's ability to maintain a patent airway independently and continuously and respond appropriately to physical stimulation and verbal commands.

The risks of intravenous conscious sedation include: inhibition of the gag reflex and concomitant risk of aspiration, cardiopulmonary complications (myocardial infarction, cardiac arrhythmias, hypoxemia), and allergic reactions to the sedative or analgesic medications. These risks are small

but real; for example, in a prospective study of 14,149 patients undergoing IVCS during upper gastrointestinal endoscopies, the rate of immediate cardiopulmonary events was 2 in 1000.[Quine *et al.*, 1995] The 30-day mortality was 1 per 2,000 cases. In this study, there was a strong association between lack of monitoring and use of high-dose benzodiazepines with adverse outcomes. There was also an association between the use of local anesthetic sprays to the oropharynx and the development of pneumonia. In order to minimize the risk of intravenous conscious sedation, only qualified personnel will be responsible for conscious sedation. A minimum of two individuals will be involved in the care of patients undergoing conscious sedation—the physician performing the biopsy procedure, and the individual (M.D. or R.N.) who monitors the patients and his/her response to both the sedation and the procedure, and who is capable of assisting with any supportive or resuscitative measures. The room where the procedure utilizing IVCS takes place will have adequate equipment to provide supplemental oxygen, monitor vital signs, and maintain an airway should this be necessary. An emergency cart will also be immediately accessible to the room where the procedure is to take place, and emergency support services will be available on page. Patients will be screened and evaluated for their fitness to undergo conscious sedation by a trained physician. Patients with active cardiac disease are excluded from this study. No local anesthetic spray to the oropharynx will be necessary, given that endoscopy is not a planned procedure. Following the procedure, patients will be observed closely in the recovery room for a minimum of 2 hours.

### **General Anesthesia**

Because of the higher risk of general anesthesia compared with local anesthesia or intravenous conscious sedation, biopsies that would require general anesthesia in order to be performed *are not permitted* on this protocol.

**For Biopsies of Soft Tissue, Liver, Bone, Breast, Etc:**

1. After biopsy is performed, the tissue mass is placed on a sterile gauze
2. Using forceps, separate the tumor tissue
3. Place 2 pieces (cores) of tumor tissue in each cassette (typically end up with 3 cassettes per biopsy); the last cassette will contain many small pieces of tumor tissue
4. Fill cassettes with OCT
  - a. Completely cover tissue
  - b. Limit the amount of bubbles
5. Place cassettes on dry ice and prepare for transport by limiting OCT leakage
6. Return samples to the lab and complete freezing of samples in OCT with dry ice (about 10 minutes freezing time)
7. Once samples are frozen, place in plastic bag; label bag with date, protocol number, patient number, and number of initials included
8. Store in -80C freezer

**For Effusions and Ascites**

1. Fluid sample should be split into two equal aliquots
2. One aliquot should be spun down into a pellet and snap frozen in an ETOH/dry ice bath or in liquid N2
3. One aliquot should be fixed and processed as a standard cell block.

Note: if the sample preparation is done by a clinical cytopathology laboratory, it is important to explain that the sample is for research purposes only and that no thin prep should be performed as this uses up a significant portion of the sample.

**For Fine Needle Aspiration Samples**

A goal of 3 passes:

1. One pass should be evacuated and rinsed directly into 2mL of room temperature Trizol for RNA analysis.
2. One pass should be evacuated and rinsed directly into 2mL of room temperature Trizol for DNA analysis.
3. One pass should be evacuated and rinsed directly into 10-20mL of RPMI to prepare a cell block.

APPENDIX C            **FACT-B Questionnaire**

Participant ID \_\_\_\_\_ Cycle# \_\_\_\_\_

Below is a list of statements that other people with your illness have said are important. Please circle or mark one number per line to indicate your response as it applies to the past 7 days.

PHYSICAL WELL-BEING		Not at all	A little bit	Some-what	Quite a bit	Very much
GP1	I have a lack of energy .....	0	1	2	3	4
GP2	I have nausea .....	0	1	2	3	4
GP3	Because of my physical condition, I have trouble meeting the needs of my family .....	0	1	2	3	4
GP4	I have pain .....	0	1	2	3	4
GP5	I am bothered by side effects of treatment .....	0	1	2	3	4
GP6	I feel ill .....	0	1	2	3	4
GP7	I am forced to spend time in bed	0	1	2	3	4
SOCIAL/FAMILY WELL-BEING		Not at all	A little bit	Some-what	Quite a bit	Very much
GS1	I feel close to my friends .....	0	1	2	3	4
GS2	I get emotional support from my family .....	0	1	2	3	4
GS3	I get support from my friends .....	0	1	2	3	4
GS4	My family has accepted my illness .....	0	1	2	3	4
GS5	I am satisfied with family communication about my illness .....	0	1	2	3	4
GS6	I feel close to my partner (or the person who is my main support) .....	0	1	2	3	4

Q1  
 GS7

*Regardless of your current level of sexual activity, please answer the following question. If you prefer not to answer it, please mark this box and go to the next section.*

I am satisfied with my sex life 0 1 2 3 4

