#### **3.1 Eligibility Criteria**

- 3.1.1 Participants must have histologically or cytologically confirmed invasive breast cancer, with metastatic disease. Participants without pathologic or cytologic confirmation of metastatic disease should have unequivocal evidence of metastasis from physical examination or radiologic evaluation.
- 3.1.2 Breast cancer must be HER2-negative by IHC or non-amplified as determined by the current ASCO-CAP criteria. If patient has more than one histological result, the most recent one will be used for inclusion. Participants may be ER/PR positive or negative.
- 3.1.3 Patients must harbor tumors with total mutational burden (TMB) of at least 9 mutations per megabase assessed by a cancer-gene panel containing more than 300 genes, and performed in a CLIA verified laboratory. Tests like Foundation One, OncoPanel (DFCI), or IMPACT (MSKCC) are acceptable for including patients on this trial.
- 3.1.4 Participants must have measurable disease by RECIST version 1.1.
- 3.1.5 Participants must agree to undergo a research biopsy, if tumor is safely accessible, at baseline and at day 29 cycle 1 (+14 scheduling window). Previously collected archival tissue will be obtained on all participants. Participants for whom newly-obtained samples cannot be provided (e.g. inaccessible or participant safety concern) may submit an archived specimen (block or if not possible, 20 unstained slides).
- 3.1.6 Prior chemotherapy: Participants may have received 0-3 prior chemotherapeutic regimens for metastatic breast cancer and must have been off treatment with chemotherapy for at least 14 days prior to study treatment initiation.
- 3.1.7 Patients with hormone receptor positive breast cancer must have progressed on at least one prior line of endocrine therapy in the metastatic setting or have disease recurrence while on adjuvant endocrine therapy.

NOTE: Participants should also be adequately recovered from acute toxicities of prior treatment, with the exception of alopecia and peripheral sensory neuropathy.

3.1.8 Prior biologic therapy: Patients must have discontinued all biologic therapy at least 14 days prior to study treatment initiation.

3.1.9 Prior radiation therapy: Patients may have received prior radiation therapy in either the metastatic or early-stage setting. Radiation therapy must be completed 14 days prior to study treatment initiation.

NOTE: In all cases, there must be no ongoing complications from prior radiotherapy.

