### 10. STUDY CALENDAR

Screening evaluations are to be conducted within 28 days prior to start of protocol therapy unless otherwise specified. Screening assessments occurring within 4 days prior to initiating study treatment do not need to be repeated on Cycle 1 Day 1.

As detailed in the Study Calendar, laboratory assessments including a negative pregnancy test in women of child-bearing potential must be documented within 7 days before the first dose of study medication.

In the event that the participant's condition is deteriorating, laboratory evaluations should be repeated within 48 hours prior to initiation of the next cycle of therapy.

Assessments must be performed prior to administration of any study agent. Study assessments and agents should be administered within  $\pm$  3 days of the protocol-specified date, unless otherwise noted.

	Screening a	Cycle 1			Cycle 2-4			Cycle 5+			End of Treatment q	Follow-Up
		Day 1	Day 15	Day 29	Day 1	Day 15	Day 29	Day 1	Day 15	Day 29		
Medical History b	X											
Physical exam c	X	X	X	X	X			X			X	
Concurrent medications d	X	X			X			X			X	
ECOG	X	X			X			X			X	
Adverse event evaluation		X	X	X	X	X	X	X	X	X	X s	
Vital signs c	X	X	X	X	X	X	X	X	X	X	X	
Hematology panel f	X	X	X	X	X	X	X	X	X	X	X	
Chemistry panel g	X	X	X	X	X	X	X	X	X	X	X	
Urine Protein Creatinine Ratio	X				X			X			X	
TSH/ft4	X	X			X			X h			X	
ACTH/Cortisol	X	X			X			X h				
Amylase and Lipase	X	X			X			X h				
Coagulation panel (PT/PTT)	X											
Pregnancy test i	X i	X i		X i	X i	X i	X i	X i	X i	X i		
12- lead EKG	X											
Tumor Assessment j	X				X			X			X k	X k
Research Blood l		X			X			X			X	X
Research Biopsy m	X			X							X	
Archival Tumor Retrieval n	X											
Quality of Life r	X				X			X				
Research Stool Collection & Questionnaire o, p (Section 9.4)	X			X							X	
Survival (Section 5.6)												X

- a. Screening assessments are to be conducted within 28 days prior to start of protocol therapy unless otherwise specified. If these screening assessments occur within 4 days before start of study treatment, then they may serve as the baseline Cycle 1 Day 1 values.

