- p. An optional stool sample may be collected at the time of grade  $\geq 2$  diarrhea after discussion with the PI. As these collections are for exploratory correlative purposes, failure to provide a sample or complete the stool questionnaires at these timepoints will not constitute a protocol violation. See section 9 and/or lab manual for stool collection and processing instructions.
- q. End of treatment visit is to occur within 30 days of final administration of study treatment. End of treatment assessments do not have to be repeated if the same assessments were performed within 7 days (28 days for tumor assessments) prior to the visit.

- r. FACT B and the Rotterdam Symptom Checklist should be completed baseline or C1D1 (any time prior to first dose), D1 of C2-C4, and then on D1 of every other cycle (C6D1, C8D1, etc.) These questionnaires may be found in Appendices C and D.
- s. An adverse event assessment is performed 100 days (-15/+30 days) after the last dose of nivolumab. This may be conducted in person or by phone by the investigator or suitably trained and qualified delegate (i.e. MD, RN, NP, etc).

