**Rotterdam Symptom Checklist**

**Confidential**

*In this questionnaire you will be asked about your symptoms. Would you please, for all symptoms mentioned, indicate to what extent you have been bothered by it, by circling the answer most applicable to you. The questions are related to the past week.*

*Example: Have you been bothered, during the past week, by*

headaches	not at all	a little	quite a bit	very much
-----------	------------	-----------------	-------------	-----------

*Have you, during the past week, been bothered by*

lack of appetite	not at all	a little	quite a bit	very much
------------------	------------	----------	-------------	-----------

irritability	not at all	a little	quite a bit	very much
--------------	------------	----------	-------------	-----------

tiredness	not at all	a little	quite a bit	very much
-----------	------------	----------	-------------	-----------

worrying	not at all	a little	quite a bit	very much
----------	------------	----------	-------------	-----------

sore muscles	not at all	a little	quite a bit	very much
--------------	------------	----------	-------------	-----------

depressed mood	not at all	a little	quite a bit	very much
----------------	------------	----------	-------------	-----------

lack of energy	not at all	a little	quite a bit	very much
----------------	------------	----------	-------------	-----------

low back pain	not at all	a little	quite a bit	very much
---------------	------------	----------	-------------	-----------

nervousness	not at all	a little	quite a bit	very much
-------------	------------	----------	-------------	-----------

nausea	not at all	a little	quite a bit	very much
--------	------------	----------	-------------	-----------

despairing about the future	not at all	a little	quite a bit	very much
-----------------------------	------------	----------	-------------	-----------

difficulty sleeping	not at all	a little	quite a bit	very much
---------------------	------------	----------	-------------	-----------

headaches	not at all	a little	quite a bit	very much
-----------	------------	----------	-------------	-----------

vomiting	not at all	a little	quite a bit	very much
----------	------------	----------	-------------	-----------

dizziness	not at all	a little	quite a bit	very much
-----------	------------	----------	-------------	-----------

decreased sexual interest	not at all	a little	quite a bit	very much

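### The baseline quality-of-life forms recall one week but may be completed up to four weeks before first dose, so early forms can reach back into prior therapy; tie them to Cycle 1 Day 1

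*Combined protocol and SAP*

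**What the plan says.** **Recall period.** FACT-B (Appendix C) reads "Please circle or mark one number per line to indicate your response as it applies to the past 7 days". The Rotterdam Symptom Checklist (Appendix D) reads "The questions are related to the past week".

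**When the first form is due.** The grid in Section 10 marks Quality of Life under Screening and not under Cycle 1 Day 1. Footnote r is looser: "FACT B and the Rotterdam Symptom Checklist should be completed baseline or C1D1 (any time prior to first dose", with the bracket closing there. The general rule is "Screening evaluations are to be conducted within 28 days prior to start of protocol therapy unless otherwise specified", and nothing shorter is specified for the questionnaires. Later forms are due on Day 1 of Cycles 2 to 4 and of every other cycle after that.

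**When prior therapy must have ended.** For chemotherapy, patients "must have been off treatment with chemotherapy for at least 14 days prior to study treatment initiation" (3.1.6). For biologics, "Patients must have discontinued all biologic therapy at least 14 days prior to study treatment initiation" (3.1.8). For radiotherapy, "Radiation therapy must be completed 14 days prior to study treatment initiation" (3.1.9). Exclusion 3.2.2 sets the same 14 days for other anti-cancer therapy.

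**What may be given during screening.** Section 5.4.1 lists systemic chemotherapy, biologic therapy and radiation other than palliative among the therapies prohibited in the Screening and Treatment Phase.

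**What the scores are for.** Objectives 1.5.1 and 1.5.2 are to assess quality of life with each instrument. Section 11.3.1.6 names the scores as the measure. Section 13 contains no quality-of-life analysis.

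**The concern.** A one-week recall describes the state of the patient only around the day the form is filled in. Every follow-up form is tied to Day 1 of a cycle, but the baseline form is allowed to float across four weeks, and the grid steers sites towards the earlier end of that allowance. Two patients in the same condition on the day of first infusion can have baselines that describe different weeks, one of which may still carry the effects of the previous regimen.

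Both instruments are sensitive to this. FACT-B asks about nausea, lack of energy and being bothered by treatment side effects. The checklist asks about vomiting and tingling in the hands or feet. Both ask about hair loss. If an early form is raised or lowered by the previous treatment, recovery from that treatment could later look like improvement on nivolumab plus ipilimumab, or hide a decline. There is no control arm to carry the same error.

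The calendar is tighter elsewhere. Physical examination, ECOG, vital signs, hematology and chemistry are marked at both Screening and Cycle 1 Day 1. Baseline stool has a 14-day window and the screening pregnancy test a 7-day one.

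**Working it through.** The plan gives no figure to reproduce here, so the check is a count of days.

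**Inputs.** First dose is day 0. The form may be completed on any day d from -28 to -1 (Section 10). The recall week is either d-7 to d-1 or d-6 to d, since the forms do not say whether the day of completion counts. The latest end of prior therapy is day -14 if only the washouts in 3.1.6 to 3.1.9 and 3.2.2 are considered. If the prohibition in 5.4.1 takes effect as screening opens on day -28, the latest end is day -29.

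**Rule.** A form touches prior therapy if its earliest recalled day is on or before the last day of therapy. It lies wholly in the prior-therapy period if its latest recalled day is on or before that day.

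| Last day of prior therapy | Recall d-7 to d-1: touches / wholly | Recall d-6 to d: touches / wholly |
|---|---|---|
| Day -14 (washout alone) | d ≤ -7: 22 of 28 / d ≤ -13: 16 of 28 | d ≤ -8: 21 of 28 / d ≤ -14: 15 of 28 |
| Day -29 (stops before a 28-day screening) | d ≤ -22: 7 of 28 / d ≤ -28: 1 of 28 | d ≤ -23: 6 of 28 / 0 of 28 |

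So 6 to 7 days (21% to 25%) are affected when therapy stops before a 28-day screening opens. The 21 to 22 days (75% to 79%) are a ceiling that requires therapy to be given during screening itself.

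For a shorter screening the affected days stay at 6 to 7 but are a larger share. If screening opens on day -14 and therapy ended on day -15, forms from day -14 to day -9 or -8 are affected, which is 6 to 7 of 14.

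**Cycle 1 Day 1.** With d = 0, the earliest recalled day is -7 or -6, at least a week after day -14, so the overlap is zero. The calendar also lets screening assessments done within 4 days stand in for Cycle 1 Day 1. A form on day -4 reaches back at most to day -11, still inside the washout.

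These counts concern days on therapy. Acute toxicity can outlast the last dose, and the documents give no basis for saying by how long.

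**The case against.** The strongest reply is Section 5.4.1. The 14-day rules are minimum washouts, not permission to treat during screening, and systemic chemotherapy and biologics are prohibited once screening begins. On that text a form in the Screening column is completed after such therapy has stopped. This stands, and it removes most of the 22-day count. It does not remove the problem: a form in the first week of screening still recalls the week before screening, the documents do not date the start of the Screening Phase for an individual patient, and palliative radiotherapy is excepted from the ban.

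Second, the note in 3.1 requires adequate recovery from acute toxicity. This helps, but it is an eligibility condition not tied to the date of the form, and it exempts alopecia and sensory neuropathy.

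Third, at sites outside DF/HCC, Section 4.3 asks for therapy within 7 days of registration, and Appendix E (3.7.2) bars protocol-specific interventions before registration is confirmed. If a questionnaire counts as such an intervention, the window there shrinks to about a week and at most one screening day, day -7, is affected. The documents do not say that it counts, the calendar lists it under Screening, and Section 4.1 sets no 7-day limit for DF/HCC sites.

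Fourth, no change-from-baseline analysis is planned, and footnote r already allows Cycle 1 Day 1. Both are true. The first limits what can be claimed about bias. The second shows that the remedy is feasible, but an option does not make the timing uniform.

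**Conclusion.** The point holds as a weakness in timing. A compliant baseline form can precede treatment by up to four weeks. Early in screening, its recall week can reach into the last week of prior therapy or its acute toxicity. Since the trial has one arm and serial forms, the baseline is the natural reference for objectives 1.5.1 and 1.5.2, and its timing should be uniform and inside the washout.

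A reader might go further and infer that 79% of screening days yield a contaminated baseline and that mean change is overstated by several points. The first figure sets aside Section 5.4.1 and puts the last therapy exactly on day -14. The second needs inputs that the documents do not contain. Assume that forms are spread evenly over 28 days, that 25% to 75% of patients come straight off therapy, and that any overlap shifts the FACT-B total by 5 to 10 points. Then 22 affected days give 0.25 × 22/28 × 5 = 1.0 to 0.75 × 22/28 × 10 = 5.9 points. Seven affected days give 0.25 × 7/28 × 5 = 0.3 to 0.75 × 7/28 × 10 = 1.9. The spread comes wholly from assumptions, and it describes an analysis that is not planned. The size of any bias cannot be derived from the documents.

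Response rate, sample size and safety are unaffected. The change is worth making because it is nearly free and because a badly timed baseline cannot be repaired at analysis.

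**What to change.** In footnote r of the Study Calendar, replace the allowance for baseline or any time before first dose with *C1D1, before the first infusion*, and move the quality-of-life mark in the grid from Screening to Cycle 1 Day 1.

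If a patient has only a screening form, use it as the baseline, flag it, and report a sensitivity summary without such forms. No data are lost.

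The cost is one footnote and one grid cell. Every treated patient attends that visit, so no visit or form is added. The downside is that a form missed on Cycle 1 Day 1 cannot be recovered unless a screening form exists, so sites should hand it out before the infusion starts.
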